4.4 END OF STUDY DEFINITION

A participant is considered to have completed the study if he or she has completed all phases of the study including the last visit or the last scheduled procedure shown in the Schedule of Activities (SoA), Section 1.3.

The end of the study is defined as completion of the last visit or procedure shown in the SoA in the trial globally.

5 STUDY POPULATION

5.1 INCLUSION CRITERIA

Patients with sarcoidosis will be screened according to the following criteria (all 3 criteria need to be met):

Clinical diagnosis of cardiac sarcoidosis according to either the

Heart Rhythm Society Diagnostic Criteria based on one of the 2 diagnosis pathways (see below):

- Histological diagnosis from myocardial tissue cardiac sarcoidosis is diagnosed in the presence of noncaseating granuloma on histologic examination of myocardial tissue with no alternative cause identified (including negative stain for microorganisms – as applicable);
- 2. Clinical diagnosis from invasive and/or non-invasive studies it is probable that there is cardiac sarcoidosis if there is (a) histological diagnosis of extracardiac sarcoidosis and (b) one or more of the following: steroid +/- immunosuppressant responsive cardiomyopathy or heart block; unexplained reduction in LVEF (<40%); unexplained sustained (spontaneous or induced) ventricular tachycardia; Mobitz type II 2nd degree or 3rd degree AV block; patchy uptake on dedicated cardiac PET (in a pattern consistent with cardiac sarcoidosis); late gadolinium enhancement on cardiac magnetic resonance (in a pattern consistent with cardiac sarcoidosis); positive gallium uptake (in a pattern consistent with cardiac sarcoidosis); positive gallium uptake (in a pattern consistent with cardiac sarcoidosis); positive gallium uptake (in a pattern consistent with cardiac sarcoidosis); positive gallium uptake (in a pattern consistent with cardiac sarcoidosis); positive gallium uptake (in a pattern consistent with cardiac sarcoidosis); positive gallium uptake (in a pattern consistent with cardiac sarcoidosis); positive gallium uptake (in a pattern consistent with cardiac sarcoidosis); positive gallium uptake (in a pattern consistent with cardiac sarcoidosis); positive gallium uptake (in a pattern consistent with cardiac sarcoidosis); positive gallium uptake (in a pattern consistent with cardiac sarcoidosis); positive gallium uptake (in a pattern consistent with cardiac sarcoidosis); positive gallium uptake (in a pattern consistent with cardiac sarcoidosis); positive gallium uptake (in a pattern consistent with cardiac sarcoidosis); positive gallium uptake (in a pattern consistent with cardiac sarcoidosis); positive gallium uptake (in a pattern consistent with cardiac sarcoidosis); positive gallium uptake (in a pattern consistent with cardiac sarcoidosis); positive gallium uptake (in a pattern consistent with cardiac sarcoidosis); positive gallium uptake (in a pattern consistent with cardiac sarcoidosis); positive gallium uptak

or the diagnostic guidelines for cardiac sarcoidosis based on New CS Guidelines in Japan (see below):

- Histological diagnosis group (those with positive myocardial biopsy findings) Cardiac sarcoidosis is diagnosed histologically when endomyocardial biopsy or surgical specimens demonstrate non-caseating epithelioid granulomas.
- 2. *Clinical diagnosis group* (those with negative myocardial biopsy findings or those not undergoing myocardial biopsy)

The patient is clinically diagnosed as having sarcoidosis:

- (1) When epithelioid granulomas are found in organs other than the heart and clinical findings strongly suggestive of the above-mentioned cardiac involvement are present (Table 1); or
- (2) When the patient shows clinical findings strongly suggestive of pulmonary or ophthalmic sarcoidosis; at least 2 of the 5 characteristic laboratory findings of a sarcoidosis (Table 2); and clinical findings strongly suggest the above-mentioned cardiac involvement (Table 1)

TABLE 1. Clinical findings defining cardiac involvement

Cardiac findings should be assess based on the major criteria and the minor criteria. Clinical findings that satisfy the following 1) or 2) strongly suggest the presence of cardiac involvement.

- (1) 2 or more of the 5 major criteria (a)-(e) are satisfied.
- (2) 1 of the 5 major criteria (a)-(e) and 2 or more of the 3 minor criteria (f)-(h) are satisfied.

- 1. Major criteria
- (a) High-grade AV block (including complete AV block) or fatal ventricular arrhythmia (e.g., sustained VT and VF)
- (b) Basal thinning of the ventricular septum or abnormal ventricular wall anatomy (ventricular aneurysm, thinning of the middle or upper ventricular septum, regional wall thickening
- (c) Left ventricular contractile dysfunction (LVEF < 50%)
- (d) ⁶⁷Ga citrate scintigraphy or ¹⁸F-FDG PET reveals abnormally high tracer accumulation in the heart
- (e) Gadolinium-enhanced MRI revealed delayed contrast enhancement of the myocardium
- 2. Minor criteria
- (f) Abnormal ECG findings: Ventricular arrhythmias (nonsustained VT, multifocal or frequent premature ventricular contractions, bundle branch block, axis deviation, or abnormal Q waves
- (g) Perfusion defects on myocardial perfusion scintigraphy (SPECT)
- (h) Endomyocardial biopsy: Monocyte infiltration and moderate or severe myocardial interstitial fibrosis

Table 2. Characteristic laboratory findings of sarcoidosis

- 1. Bilateral hilar lymphadenopathy
- 2. High serum angiotensin-converting (ACE) activity or elevated serum lysozyme levels
- 3. High serum soluble interleukin-2 receptor (sIL-2R) levels
- 4. Significant tracer accumulation in 67Ga citrate scintigraphy or 18F-FDG PET
- 5. A high percentage of lymphocytes with a CD4CD8 ration of >3.5 in BAL fluid.

or the Diagnostic guidelines for isolated cardiac sarcoidosis based on New CS Guidelines in Japan

Diagnostic guidelines for isolated cardiac sarcoidosis

Prerequisite

- No clinical findings characteristic of sarcoidosis are observed in any organs other than the heart. (The patient should be examined in detail for respiratory, ophthalmic, and skin involvement of sarcoidosis. When the patient is symptomatic, other etiologies that can affect the corresponding organs must be ruled out.)
- 4. ⁶⁷Ga scintigraphy or ¹⁸F-FDG PET reveals no abnormal tracer accumulation in any organs other than the heart.
- 5. A chest CT scan reveals no shadow along the lymphatic tracts in the lungs or no hilar and mediastinal lymphadenopathy (minor axis>10 mm).
- Histological diagnosis group Isolated cardiac sarcoidosis is diagnosed histologically when endomyocardial biopsy or surgical specimens demonstrate non-caseating epithelioid granulomas.
- (2) Clinical diagnosis group Isolated cardiac sarcoidosis is diagnosed clinically when criterion (d) and at least 3 other major criteria (a)-(e) are satisfied. (Table 1)

2. Cardiac fluoro-deoxyglucose uptake on recent PET (performed within the prior 60 days)

3. CRP high-sensitivity assay ≥2 mg/l (performed within the prior 60 days)

4. On stable medical therapy for cardiac sarcoidosis for at least 30 days prior to randomization

5.2 EXCLUSION CRITERIA

Subjects will not be eligible if they meet any one of the following exclusion criteria.

- 1. Age<21 years;
- 2. Pregnancy;
- 3. Inability to obtain consent from patient or legally authorized representative;
- 4. Contraindications to treatment with Anakinra (Kineret)(i.e. prior allergic reaction to the drug or to E. coli derived products or severe allergy to latex);
- 5. Severe anemia (*Hgb<8 g/dl due to the need of more frequent blood sampling with this study*).
- 6. Acute or chronic active infections (not including treated/cured HCV with negative viral load).
- 7. Acute or chronic inflammatory disease other than sarcoidosis.
- 8. Treatment with Tumor Necrosis Factor- α blockers.
- 9. Active acute or chronic psychiatric illness that in the opinion of the investigator may prevent from complying with study instructions;
- 10. Limited English Proficiency that in the opinion of the investigator may prevent from understanding the content of the informed consent form or safely completing the study procedures.
- 11. Live vaccination within the prior month
- 12. Neutropenia (defined as absolute neutrophil count < 1,500/ml or <1,000/ml if subject is African American)
- 13. History of malignancy within the prior 5 years (with exception of basal cell skin cancer, carcinoma in-situ of the cervix or low risk prostate cancer after curative therapy)
- 14. Participation in another concurrent intervention study within 30 day or treatment with an investigational drug within 5 half-lives prior to randomization
- 15. Severe kidney disease (GFR <30 mL/min/1.73m²)
- 16. Evidence of COVID-19 within the last 60 days or recent (21 days) exposure to close personal contact with COVID-19.
- 17. [Chronic, moderate-to-severe kidney disease (GFR <60 mL/min/1.73m²) or acute kidney injury, or history of severe hypersensitivity reactions to gadolinium-based contrast agents] For VCU Imaging Substudy

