7 STUDY INTERVENTION DISCONTINUATION AND PARTICIPANT DISCONTINUATION/WITHDRAWAL

7.1 DISCONTINUATION OF STUDY INTERVENTION

Reasons for discontinuation of treatment

Reasons for discontinuation of Anakinra:

- Systemic infection (sepsis)*;
- Surgery*;
- New diagnosis of cancer that requires local or systemic treatment;
- Hypersensitivity reaction (rash, anaphylaxis, arthritis);
- Severe injection site reactions*;
- Need for immunosuppressant therapy or treatment with a biologic agent (i.e. TNF-alpha blocker);
- Acute myocardial infarction or stroke*;
- Severe neutropenia (<1,000/mm3) if there is a perception of increased infectious risk by the provider*.

In the cases labelled by * treatment may be restarted by investigators after the condition is resolved.

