8.2.2 Risks reduction strategies for Anakinra treatment

The risks associated with anakinra appear to be mostly related to risk of infection (1.8% vs 0.6% of serious infections in a rheumatoid arthritis study¹⁸), and injection site reactions. To better estimate the risk, one needs to place the estimates in context: the estimated 2% risk of serious infection with anakinra quoted in the FDA approved package insert refers to the use of anakinra/Kineret as second line agent for the treatment of rheumatoid arthritis, in which anakinra was used in addition to corticosteroids or other disease-modifying agents further increasing infectious risk. The risk of infection of anakinra monotherapy is not known, but it does not appear to be high. In a study cohort of patients with Neonatal Onset Multisystem Inflammatory Disease, another autoinflammatory condition for which anakinra is indicated, no dose limiting toxicities were reported for anakinra over the 148.1 patient-year study period: there were only 3 serious infections reported (2 wound infections and 1 gastroenteritis) and in all 3 cases, treatment with anakinra was considered possibly related to the event, however treatment was not discontinued and patients improved with antibiotics. Moreover, if one considers the 'excess risk' of serious infection with anakinra to evenly distributed through the year, a treatment of 1 month, would lead to an excess risk that is less than then 1.2% difference reported in the prescribing information. Nevertheless, the inherent antiinflammatory activity of anakinra may potentially mask some of the signs of infection such as fever and leukocytosis. In the CANTOS trial, canakinumab, another IL-1 blocker was associated with a 0.1% excess risk of life-threatening infection per year compared with placebo – canakinumab, at difference with anakinra, is long-acting and it cannot be stopped in case of infection, and therefore one would consider the risk of life-threatening infections with anakinra given for 1 month to be 10-fold lower than canakinumab for 1 year.

To reduce the risk of infections with anakinra we plan to follow the following strategies:

- Exclude patients with acute or chronic infections at time of screening;
- Exclude patients on TNF-alpha blockers;
- Exclude patients who are neutropenic;
- Educate patients on the possibility that symptoms or signs of infections may be less evident with taking the investigational drug;

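### Exclusion 12 gives its neutrophil limits per ml and section 7.1 gives its limit per mm3; the units differ 1,000-fold and need reconciling

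*Combined protocol and SAP*

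**What the plan says.** Two places in the protocol put a number on the neutrophil count.

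- Section 5.2, exclusion 12, which defines neutropenia: "absolute neutrophil count < 1,500/ml or <1,000/ml if subject is African American". Both limits are per ml.
- Section 7.1, reasons for discontinuing anakinra: "Severe neutropenia (<1,000/mm3) if there is a perception of increased infectious risk by the provider". This limit is per mm3 and carries a second condition, the provider's view of infectious risk. The item is starred, so treatment may be restarted once the condition has resolved.

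Sections 2.3.3 and 8.2.2 both list the exclusion of neutropenic patients among the measures against infection ("Exclude patients who are neutropenic"). Neither gives a number or a unit, so both depend on exclusion 12 for the definition. None of the listed amendments mentions the neutrophil limit.

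**The concern.** The entry rule and the stopping rule concern the same laboratory value, yet their limits are written in units that differ by three orders of magnitude. On the literal text, the count that bars a patient from entry lies hundreds of times below the count that the protocol calls severe once treatment has begun.

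This is operative text. Excluding neutropenic patients is one of five infection-risk measures in section 8.2.2. The protocol lists neutropenia as a side effect of anakinra, says that the drug may mask fever and leukocytosis, and allows background steroids and methotrexate (sections 2.3.1, 8.2.1 and 6.5). Eligibility criteria are applied and audited as written. If the literal unit were copied into an eligibility form or a range check, that check would not do what sections 2.3.3 and 8.2.2 intend.

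The second limit is not a rare case. In the planning cohort in section 9.2, 77% of patients were African American, and section 3 targets more than 30% African American enrollment.

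**Working it through.** The plan states no derived figure to reproduce. The check is a unit conversion.

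**Inputs**

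- General entry limit: 1,500 per ml (section 5.2, exclusion 12).
- Entry limit for African American patients: 1,000 per ml (same item).
- Severe neutropenia: 1,000 per mm3 (section 7.1).
- Conversion: 1 ml = 1 cm3 = 1,000 mm3, so count per mm3 = count per ml / 1,000.

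**Limits on a common unit**

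| Limit | As written | Per mm3 | Per ml | 7.1 limit divided by this limit |
|---|---|---|---|---|
| Exclusion 12, general | 1,500/ml | 1,500 / 1,000 = 1.5 | 1,500 | 1,000 / 1.5 = 666.7 |
| Exclusion 12, African American | 1,000/ml | 1,000 / 1,000 = 1.0 | 1,000 | 1,000 / 1.0 = 1,000 |
| Section 7.1 | 1,000/mm3 | 1,000 | 1,000 × 1,000 = 1,000,000 | 1 |

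The factor of 1,000 is exact for the units and for the African American limit. For the general limit against section 7.1 the ratio is about 667, because the numerals also differ (1,500 against 1,000).

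**Where the literal rules conflict**

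Read literally, exclusion 12 passes any patient at or above 1.5/mm3 (1.0/mm3 if African American). Every count from there up to 1,000/mm3 therefore passes at entry while lying below the level that 7.1 calls severe. For example, 500/mm3 = 500 × 1,000 = 500,000/ml, which is far above 1,500/ml and so is not excluded, yet is half the 7.1 limit.

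**If the exclusion figures were per mm3**

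The limits would be 1,500/mm3 and 1,000/mm3 (1,500,000/ml and 1,000,000/ml), on the same scale as section 7.1. This shows only that a change of unit would remove the mismatch of scale. It does not establish which limits were intended.

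**What cannot be computed**

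The documents give no distribution of neutrophil counts in this population, so the share of patients who would be excluded, or wrongly passed, cannot be estimated.

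**The case against.** Three objections have weight.

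1. **The unit may be an artefact of reading the PDF.** The point rests on one letter. If the source has a micro sign, 1 µl = 1 mm3 and the two sections already share a unit. Special characters do go astray in this text: in the halting-rule list in section 10.1.7 an arrow reads as the letter à, where the same list in sections 7.2 and 9.4.4 has a comma, and section 2.3.3 has a plain letter a in TNF-a. Against this, a Greek alpha survives in exclusion 8, in the same list as exclusion 12. An artefact is possible but not shown, and the source page would settle it.

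2. **In context the meaning is fairly clear.** Exclusion 12 opens with the word neutropenia, sections 2.3.3 and 8.2.2 state the aim, and the numerals fit the scale of section 7.1. A clinician may well read past the unit. A reader might infer that the safeguard has been disabled and that the criterion excludes almost nobody. The documents do not support that: it describes the literal text only, and nothing shows how sites apply the limit. Section 10.1.9.1 mentions automatic range checks but gives no neutrophil limit. Active infection is also excluded separately (exclusion 6), and patient education and 24/7 telephone access remain.

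3. **Section 7.1 is conditional.** A reader might infer that a patient at 500/mm3 could enter while already meeting a reason to stop. That goes too far. Such a patient meets the count part of the item, but the provider must also perceive increased infectious risk.

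These objections limit the consequences that can be claimed. Unless the source page shows a micro sign, they do not remove the contradiction, because no other place in the protocol restates the numeric limits.

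**Conclusion.** The contradiction holds for the text as read. Exclusion 12 and section 7.1 use units that differ by a factor of 1,000, and the entry limits as written lie about 667 and 1,000 times below the count that 7.1 calls severe neutropenia. This is most likely a unit slip in an operative eligibility criterion. It is worth correcting because a named safety measure depends on it.

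The conclusion assumes that the letter in the extracted text matches the source page. It is no evidence that neutropenic patients have been or would be enrolled. Sample size, power, endpoints and analysis do not depend on it.

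**What to change.** 1. Check exclusion 12 on the source page. If it shows a micro sign, the units agree and no amendment is needed on this point.
2. If it reads per ml, reconcile exclusion 12 and section 7.1 to one stated unit and have the clinical team confirm the intended limits. No threshold is proposed here.
3. Confirm that the eligibility form and any database check on the neutrophil count use that same unit.

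The cost is a one-line correction at the next amendment and a short check of the form and database. No analysis needs to change.

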5.3 LIFESTYLE CONSIDERATIONS

There are no specific lifestyle considerations of restrictions required of patients during this study.

5.4 SCREEN FAILURES

Screen failures will not be included in the trial. Reasons for screening failure will be recorded. Individuals who do not meet the criteria for participation in this trial (screen failure) because of may be rescreened if the subsequently meet all inclusion criteria and do not have any exclusion criteria. Rescreened participants will be assigned a new participant number.

5.5 STRATEGIES FOR RECRUITMENT AND RETENTION

Virginia Commonwealth University

The VCU Sarcoidosis Clinic is an interdisciplinary, collaborative clinic established in 2014. [name] is a founding member of this clinic, which provides sarcoidosis patients evaluation by cardiology, pulmonary, and rheumatology specialists. The VCU Sarcoidosis Clinic was recognized as a World Association for Sarcoidosis and Other Granulomatous Disorders (WASOG) Sarcoidosis Clinic in 2017. The multidisciplinary approach is unique in the region and one of only a few such clinics nationwide. The clinic provides care to a large volume of sarcoidosis patients in Richmond and Central Virginia and receives referrals from throughout the mid-Atlantic region. Since 2010, VCU has treated more than 1600 individual sarcoidosis patients in 12,160 patient encounters.

[name] has a dedicated cardiac sarcoidosis clinic each week, to our knowledge the only such clinic in the country. Over the past 4 years, [name] has enrolled 80 patients from the Sarcoidosis Clinic to participate in the Cardiac Sarcoidosis Consortium prospective registry. Of the more than 20 international sarcoidosis centers, VCU is in the top 2 for patient enrollment to the registry. In 2016, [name] enrolled 25 CS patients to participate in a prospective study evaluating circulating fibrocytes. Based on clinic volume and track record of patient enrollment, we feel we can recruit 8-10 patients per year to participate in the current study. We will monitor recruitment and we will quickly intervene to add referrals from nearby providers if needed. [name], University of Virginia Cardiac Electrophysiologist, has committed to support the study with patient referrals from the Charlottesville region.

University of Michigan

The University of Michigan Sarcoidosis Clinic is also recognized as a WASOG Sarcoidosis Clinic. Our team of physicians, which includes UMich investigators, Drs. [name] and [name], works in concert to provide expert care to patients with this multi organ disease. It is a collaboration of providers from cardiac

electrophysiology and heart failure, as well we pulmonology, rheumatology, dermatology, and others. Cardiac patients are discussed at monthly cardiac sarcoidosis conferences, during which electrophysiologists, heart failure specialists, pulmonologists, and radiologists review cases and develop diagnostic and treatment plans for the reviewed patients. Due to the relatively high volume of the patients diagnosed with this rare disorder through the concerted effort of the physicians in the Sarcoidosis Clinic, UMich has enrolled almost 100 patients in the prospective International Cardiac Sarcoidosis Registry. A significant number of patients, who are strongly suspected of having the disorder due to their clinical presentation and imaging studies, but who lack the pathognomonic tissue biopsy, are also followed. Based on the clinic volume of the cardiac sarcoidosis patients and the interest of a number of physicians from various specialties, we feel confident that we will be well suited to enroll at least 8-10 patients annually in the proposed pilot study.

Retention Strategies

The patients are regularly followed in clinic and will be chosen for their compliance. The proposed study is also designed to be short, only 4 weeks. All study participants will receive cards with 24-hour/7-day contact number for study team members. This approach has been sufficient to achieve a 90% retention on average in prior studies of IL-1 blockade in HF at VCU. We will also implement a patient reimbursement for each completed study visit up to \$100 for the completion of all study visits. We believe this may overcome some financial barriers that our patients at VCU Health and Michigan Medicine (formerly University of Michigan Health System) may experience related to the time and cost of travel. We will collect data on enrollment and retention barriers to help enhance the success of a future

6 STUDY INTERVENTION

6.1 STUDY INTERVENTION(S) ADMINISTRATION

6.1.1 STUDY INTERVENTION DESCRIPTION

We will select 28 patients and randomly assign them to treatment with anakinra 100 mg subcutaneously daily on top of standard of care or standard of care only for 4 weeks (1:1 ratio).

